2.4.4. SUBGROUP ANALYSIS

The following subgroup analyses for the main analysis of the primary outcome (ie. the analysis using the measurements available, with values < 1.5mm on the mITT population) will be provided:

- Age (\leq / $>$ median)
- Sex (Males/Females)
- Baseline cIMT tertile
- Existing CV Disease (Yes/No)
- Duration of diabetes (\leq / $>$ median)
- Baseline HbA1c (\leq / $>$ median)
- Baseline BMI (\leq / $>$ median)
- Smoker status (Never / Ever)
- LDL cholesterol (\leq / $>$ median)
- SBP (\leq / $>$ median)
- Pump User (Yes/No)

2.4.5. OTHER SAFETY OUTCOMES

2.4.5.1. STUDY TREATMENT

The number of doses of study medication that were taken throughout the entire study (ie. from the date of randomisation to the last treatment visit attended) will be calculated as the total number of doses supplied – the total number of doses returned and will be summarised as a whole and by treatment group.

The number of subjects down-titrating and permanently discontinuing study medication during the study will be summarised overall and by treatment group, along with the reasons for down-titration and discontinuations. Time to permanent discontinuation will also be summarised.

Differences between the two treatment groups in terms of permanent withdrawals of study medication will be tested using Chi-squared tests. No other formal statistical testing will be applied.

2.4.5.2. ADVERSE EVENTS OF MEDICAL INTEREST

Adverse events of medical interest have been defined as:

- Gastrointestinal
 - diarrhoea
 - abdominal pain
 - nausea and vomiting
 - constipation
 - loss of appetite

- Any revascularisation:
 - coronary (angioplasty/stent/CABG)
 - carotid (endarterectomy)
 - peripheral (angioplasty/stent/surgical)
- Foot (left/right)
 - Ulceration
 - amputation – digit, below knee, above knee
 - ulcer debridement
- Eye (left/right)
 - laser treatment
 - vitrectomy
 - cataract surgery
 - vitreous haemorrhage
 - retinal vein or artery occlusion
 - loss of vision in one eye
- Neurological
 - Headache
- Metabolic
 - reduction in eGFR of > 25%
- Other
 - Hypersensitivity reaction to metformin
 - Overdose

The total number (and subjects experiencing at least one) adverse events of medical interest will be summarised. The type, duration, outcome, relationship to study drug and seriousness will also be summarised for all adverse events of medical interest.

A by subject listing of adverse events of medical interest will also be provided.

No formal statistical testing will be applied.

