i) Hypoglycaemia management plan: Symptoms of hypoglycaemia include paleness, shaking, perspiration, a feeling of weakness, increased heart rate, hunger, agitation, difficulty in concentrating, irritability, fatigue, blurred vision, temporary loss of consciousness, confusion, convulsions and coma (see http://www.sdrm.org.uk/sites/default/files/sop27_managementofhypoglycaemia.pdf).

Participants will be asked to record all hypoglycaemic episodes on the relevant page in their Study Diary. Throughout the trial they will be encouraged to check their blood sugar if they feel hypoglycaemic and record the result. However, they should not delay treating symptoms if their blood sugar meter is not readily available. All major (severe) hypoglycaemia should be reported to the Investigator/ nurse team within 24 hours during the metformin dose titration phase of the study (see page 27 below). Contact should be maintained with the participant so that insulin dose can be adjusted appropriately. A hypoglycaemic event will be defined as “an event which causes the symptoms of hypoglycaemia at any level of blood glucose measurement or a blood glucose measurement of less than 2.8.mmol/l with or without symptoms.”

Hypoglycaemic events will be categorised into minor, major episodes and any involving unconsciousness as follows:

- **Minor episodes** are treated by the participant and will be resolved by eating some short acting glucose source, followed by a longer acting carbohydrate.
- **Major (or severe) episodes require assistance from** one or more other persons to resolve the event e.g. another family member or paramedic.
- **Major (or severe) episodes involving unconsciousness** (self-reported)

All episodes of severe hypoglycaemia should be reported to study nurses as soon as possible in order that the hypoglycaemia management plan can be followed.

As in the study by Lund et al,¹⁸ we will also record information on self-reported blood/ plasma glucose levels during hypoglycaemic events as captured from the Study Diary.

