related to the study endpoints. All Serious Adverse Events with exception of planned routine hospitalisations and outpatient hospital visits will be collected within the eCRF.

Adverse Events of Medical Interest

- **Hypoglycaemia:** as per the Steno Hypoglycaemia Questionnaire (Appendix 3) administered at study visits as per the Schedule of Assessments
- **Gastrointestinal:** Diarrhoea, abdominal pain, nausea and vomiting, constipation, loss of appetite resulting in discontinuation of study medication or dose reduction.
- **Cardiovascular:** chest discomfort, palpitations resulting in discontinuation of study medication or dose reduction
- **Any revascularisation:** coronary (angioplasty/ stent/ CABG); carotid (endarterectomy); peripheral (angioplasty/ stent/ surgical)
- **Foot:** ulceration; lower limb surgical procedure: amputation (digit/ below knee/ above knee); ulcer debridement.
- **Eye:** laser treatment; vitrectomy; cataract surgery; vitreous haemorrhage; retinal vein or artery occlusion; loss of vision in one eye.
- **Neurological:** headache resulting in discontinuation of study medication or dose reduction
- **Metabolic:** biochemically-confirmed unexplained acidosis with lactate > 5.0 mmol/L, abnormal LFTS results >2.5 times upper limit of normal, or reduction in eGFR of > 25%
- **Other:** hypersensitivity reaction to metformin, overdose"

As outlined above, the following symptoms **should only be reported as AEs if leading to an SAE or treatment dose reduction/ discontinuation:**

- diarrhoea, abdominal pain, nausea and vomiting, constipation, loss of appetite
- taste disturbance, abnormal stools, nail disorder, rash
- increased sweating, chills, flu syndrome, flushing, skin reactions
- chest pain, palpitations
- headache, myalgia, light-headedness

At all study visits patients will be questioned about any illnesses, hospitalisations and the expected adverse reactions/ events listed above. Completion of patient diaries will aid the research team to elicit adverse events. In addition to adverse event data, at annual visits we will measure liver function tests (AST, ALT and γ GT) and a Full Blood Count.

Full details of AEs of medical interest and SAEs including the nature of the event, start and stop dates, severity, relationship to study drug and outcome will be recorded in the subject's medical records and in the eCRF. AEs will be monitored and followed up until satisfactory resolution or stabilization.

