Premature withdrawal, treatment non-adherence and other protocol deviations will be summarised by treatment group without formal statistical comparison. The primary analysis will be repeated for the subgroup of patients that completed the study according to the protocol. Adverse events will be summarised by treatment group, as a whole and by MedDRA system organ class and preferred term, without formal statistical comparison. For the purposes of analysis, visit attendance out with three weeks of the intended study visit date will constitute a protocol deviation.

A full Statistical Analysis Plan covering all study outcomes will be created and signed off before study close-out and unblinding.

The RCB and the Glasgow Clinical Trials Unit (GCTU) within which it sits, have significant experience of coordinating and analysing clinical trials. All aspects of the study will be conducted to satisfy GCTU standard operating procedures that are compliant with existing guidelines and regulations for the conduct of clinical trials. GCTU has UKCRN registration and all aspects of data management and statistical analysis will be conducted in accordance with ISO 9001:2008 for quality systems and TickIT for software development.

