1.6.4. DEVIATIONS TO THOSE SPECIFIED IN THE PROTOCOL

The biomarker sample assays will be received after the database lock and therefore are not covered by this SAP, but will be detailed in a future SAP.

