2.4.2. SECONDARY & TERTIARY OUTCOMES

The secondary outcome measures include:

- DCCT-aligned HbA1c (local assays);
- LDL cholesterol (central assay);
- Albuminuria (as per Protocol Appendix 5.0)
- Estimated glomerular filtration rate (eGFR) (ml/min/1.73m² by MDRD equation);
- Retinopathy stage (ETDRS) (two or more step progression, concatenated score from baseline);

- Weight (kg);
- Insulin dose per 24 hours per kg (units/kg);
- Endothelial function (Reactive Hyperaemia Index by peripheral arterial tonometry).*

*This measurement is only collected in a subset of centres with available equipment.

Each of the above secondary outcome measures will be analysed separately and the individual results will be reported. The protocol has a pre-defined composite interpretation of all secondary outcomes, where results will be considered as clinically meaningful with the potential to influence clinical practice only in the event that a statistically significant improvement in two or more of the individual secondary outcomes is observed on metformin.

Tertiary outcomes include:

- Frequency of major hypoglycaemia (per patient-year) (Steno Questionnaire);
- Frequency of minor hypoglycaemia (per patient-year) (Steno Questionnaire)
- Treatment satisfaction (Diabetes Treatment Satisfaction Questionnaire);
- Progression of averaged maximal distal IMT of the common carotid artery at 12, 24 and 36 months;
- Occurrence of biochemical Vitamin B12 deficiency, defined as values of vitamin B12 < 150pmol/L reported in the lab data in the eCRF.

All secondary and tertiary outcomes will be analysed using the relevant mITT analysis set.

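### SAP 2.4.5.2 omits the protocol's Cardiovascular group, 'major' hypoglycaemia is not split by unconsciousness, and 2.4.5.3 leaves either the all-AE or the patient-level SAE table unspecified

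*SAP*

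**What the plan says.** **Adverse events of medical interest.** Protocol section 13 lists nine groups. One is Cardiovascular: "chest discomfort, palpitations resulting in discontinuation of study medication or dose reduction". SAP 2.4.5.2 begins "Adverse events of medical interest have been defined as" and then lists seven groups, with no Cardiovascular one. For the listed events it provides event and subject totals, then type, duration, outcome, relationship to study drug and seriousness. SAP 1.6.4, on deviations from the protocol, mentions only the deferred laboratory work: "The biomarker sample assays will be received after the database lock and therefore are not covered by this SAP".

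**Hypoglycaemia.** Protocol 7.3(i) says "Hypoglycaemic events will be categorised into minor, major episodes and any involving unconsciousness as follows". The third category is "Major (or severe) episodes involving unconsciousness". Protocol Appendix 3 has one count line for major events without coma and another for major events with coma. SAP 2.4.2 has "Frequency of major hypoglycaemia (per patient-year) (Steno Questionnaire" and a matching minor rate. SAP 2.4.5.4 lists major hypoglycaemic events as a single item.

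**MedDRA table.** Protocol section 15 says "Adverse events will be summarised by treatment group, as a whole and by MedDRA system organ class and preferred term". The only SAP sentence with that classification is the second one of 2.4.5.3, headed Serious Adverse Events. It counts patients with at least one adverse event, by arm, for all events and by System Organ Class (SOC) and Preferred Term (PT). The word serious does not appear in that sentence, but it does in the sentences just before and after it.

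**The concern.** A programmer builds safety tables from the SAP's explicit lists. Where a list is worded as a definition and lacks a group the protocol designates, the total of adverse events of medical interest is incomplete and nothing in the output shows it. Participants are selected for cardiovascular risk, so chest symptoms that lead to stopping or reducing treatment are events a reader of the safety report would look for.

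Hypoglycaemia raises a related question, because insulin is titrated towards a tight target in both arms. Unconsciousness is the most severe form the trial records. If it is shown only inside 'major', two arms with equal major rates could differ in how severe the episodes were, and the report would not show it. The SAP also does not say that its major rate sums the two Appendix 3 lines, so the definition of a tertiary outcome is left to be inferred.

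The 2.4.5.3 sentence matters because two people could program it differently and each could defend the result.

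**Working it through.** No figure in the plan is at issue, so the check is a comparison of lists.

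**Step 1: the nine protocol groups against the SAP.**

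| Protocol section 13 group | SAP 2.4.5.2 | Elsewhere in the SAP |
|---|---|---|
| Hypoglycaemia | no | 2.4.2 (major and minor rates), 2.4.5.4 (major) |
| Gastrointestinal | yes | |
| Cardiovascular (chest discomfort, palpitations) | **no** | **no named item** |
| Revascularisation | yes | |
| Foot | yes | |
| Eye | yes | |
| Neurological (headache) | yes | |
| Metabolic | eGFR fall only | acidosis and LFTs in 2.4.5.4 |
| Other | yes | |

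9 − 7 = 2 groups are absent from 2.4.5.2. One of them, Hypoglycaemia, is picked up elsewhere. That leaves one, Cardiovascular. Acute coronary syndrome (2.4.5.4) and revascularisation (2.4.5.2) are different events and do not replace it.

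**Step 2: indirect routes for the Cardiovascular group.** There are three.
- SAP 2.4.5.1 summarises down-titrations and permanent discontinuations by arm, "along with the reasons for down-titration and discontinuations". Every event in the group has led to one or the other. The documents do not show whether the reason codes identify chest symptoms, and this summary carries no duration, outcome, relationship or seriousness.
- Serious cases enter the SAE tables.
- If the 2.4.5.3 sentence covers all adverse events, non-serious cases would appear there by PT.

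The first route was evidently not meant to replace the list. In Protocol section 13 the gastrointestinal events and headache carry the same condition of discontinuation or dose reduction, and SAP 2.4.5.2 keeps both.

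**Step 3: hypoglycaemia.** Protocol 7.3(i) names three categories, and Appendix 3 gives unconsciousness its own count. SAP 2.4.2 and 2.4.5.4 use major and minor only. Both protocol places label the unconscious episodes as major, so they presumably fall within the SAP's major category. The SAP does not say so and does not show them separately. The SAE tables would not reliably separate them either: under Protocol 7.3(i), a major episode brought to the Emergency Department counts as an SAE only if the stay exceeds 12 hours.

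**Step 4: the two readings of the 2.4.5.3 sentence.**
- If it means serious events, the all-AE table of Protocol section 15 is not specified. Recorded non-serious events outside the 2.4.5.2 list, such as rash, myalgia or taste disturbance leading to a dose change, then have no dedicated table.
- If it means all adverse events, the SAP specifies no count of patients with an SAE and no SAE table by SOC and PT. The first sentence of 2.4.5.3 counts events, not patients.

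One table is missing on each reading.

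**Step 5: MCV.** Protocol section 8 records four types of abnormal laboratory finding as AEs: LFTs, eGFR, Hb, and MCV above 105 fL. SAP 2.4.5.4 names the first three. SAP 2.4.5.6 summarises the remaining blood tests by arm and visit and counts subjects with clinically significant values. Only the cut-off is unnamed.

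**The case against.** A reader might infer that all these harms would be collected and then not reported by arm, or have no analysis at all. The documents do not support that.
- SAP 1.6.2 requires all study data to be summarised by treatment group.
- MCV is summarised by arm under 2.4.5.6, and the vitamin B12 risk is analysed directly in 2.4.2 and 2.4.5.4.
- Episodes with unconsciousness are labelled major, so they sit inside a category reported by arm. The protocol's tertiary endpoint is simply the frequency of hypoglycaemia, and no protocol text promises a separate analysis of unconsciousness.
- Taken literally, the 2.4.5.3 sentence is the all-AE table.
- Chest symptoms that led to stopping or reducing treatment could appear among the reasons in 2.4.5.1. Protocol section 8 classes these effects as very rare, below 1 in 10,000. With 379 + 50 = 429 participants in Appendix 6, or about 215 per arm, that is fewer than 215 × 0.0001 ≈ 0.02 drug-related cases per arm.
- SAP section 4 provides for a dummy report for external review before lock. Its table shells are not in the documents and may already deal with these points.

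Most of this stands, and it limits the point to a minor one. It does not remove it. The general rule in 1.6.2 defines no category or table, while 2.4.5.2 is an explicit definition and will be followed. The very-rare class describes drug reactions, whereas the list counts events whatever their cause, in people chosen for cardiovascular risk. The literal reading of 2.4.5.3 supplies one table only by leaving the other out. On unconsciousness, the split is a reasonable request because the category is defined and collected; it is not a breached commitment.

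**Conclusion.** The point holds in a limited form and is minor. There is one clear, undeclared omission: the Cardiovascular group, one of nine, is absent from the SAP's definition, so the total of adverse events of medical interest would be incomplete. One separately collected category, major hypoglycaemia with unconsciousness, is pooled and not shown. One sentence leaves either the all-AE table or a patient-level SAE table unspecified. The missing MCV cut-off is a matter of wording, since the test itself is summarised by arm.

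It would go too far to say that these harms are unanalysed or hidden from comparison by arm. It would also go too far to put a number on the events affected, because the documents give no rate for hypoglycaemic unconsciousness and no observed rate for chest symptoms.

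The conclusion assumes that the SAP's lists are programmed as written and that the dummy report does not already fill the gaps. No efficacy inference and no clinical management depends on it.

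**What to change.** 1. In SAP 2.4.5.2, restore the Cardiovascular group with the protocol's condition (events leading to discontinuation or dose reduction). If its removal was intended, declare that in 1.6.4.
2. In SAP 2.4.2, state that the tertiary major rate sums the two Appendix 3 lines. In 2.4.5.4, show major hypoglycaemia with and without unconsciousness by arm, as number of events and number of participants.
3. In SAP 2.4.5.3, specify two tables by arm, each by SOC and PT with number and percentage of patients: one for all recorded adverse events, serious and non-serious, and one for SAEs.
4. Optionally, name MCV above 105 fL as the cut-off in 2.4.5.4 or 2.4.5.6.

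The cost is a few lines of SAP text and some table rows. The protocol already provides for collecting these data, and no new testing is needed. The downside is slightly longer safety output. The dummy report is a natural place to check that the rows are there.

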2.4.5.3. SERIOUS ADVERSE EVENTS

The number of serious adverse events will be reported overall and by treatment group for any event, and by classifications of expectedness, relationship to study medication, severity and outcome.

The number and percentage of patients experiencing at least one adverse event will be reported overall and by treatment group for all events, and for events classified by MedDRA System Organ Class and Preferred Term.

A by subject listing of serious adverse events will also be provided.

Listings of all deaths will also be provided.

2.4.5.4. EVENTS OF PARTICULAR INTEREST

Events of particular interest have been defined as:

- Lactic acidosis
- ALT > 3 times upper limit of normal
- eGFR < 30 ml/min/1.73m²
- Major hypoglycaemic events

- Renal dysfunction (eGFR < 45 ml/min/1.73m² or reduction in eGFR > 25%)
- LFTs > 2.5 times upper limit of normal
- Hb < 10.0 g/dL and fall > 1.5 g/dL from baseline
- Occurrence of clinically relevant Vitamin B12 deficiency, defined as values < 110pmol/L reported in the lab data recorded in the eCRF
- Acute coronary syndrome

These events will be grouped according to whether they warrant discontinuation of study medication or not. The first three events above (lactic acidosis, ALT and eGFR < 30 ml/min/1.73m²) all warrant discontinuation of study medication.

The number and percentage of events of particular interest will be reported. For the events warranting discontinuation of study medication, the number of events occurring whilst taking study medication will be summarised along with these number of events that resulted in discontinuation.

The number and percentage of subjects experiencing at least one event for any and each specific event will also be summarised.

No formal statistical testing will be applied.

2.4.5.5. VITAL SIGNS

SBP, DBP and heart rate will be summarised as a whole, by treatment and by visit. Changes from baseline will also be summarised. Formal statistical comparisons of the changes will be made between the treatment groups using a baseline adjusted ANCOVA.

2.4.5.6. BLOOD TESTS

To identify any potential safety signal, blood tests not included as secondary or tertiary outcomes will be summarised as overall, by treatment group and by visit. Changes from baseline will also be summarised. Formal statistical comparisons of the changes shall be made between the treatment groups using a baseline adjusted ANCOVA. Any laboratory results with evidence of non-Normality of their distribution will be transformed appropriately prior to analysis.

The number of subjects with values of clinical significance will be summarised at each visit for each blood test as appropriate.

3. DOCUMENT HISTORY

This is version 1.1 of the Statistical Analysis Plan (SAP) for the REMOVAL study. The following updates were made to version 1.0:

1. Include pre-specified subgroup analysis for the main primary outcome analysis in section 2.4.4.
2. Slight clarification to the wording of the primary outcome model.

4. TABLES, FIGURES AND LISTINGS

A dummy report will be provided for external review prior to study lock.
